## 20.1 ANALYSIS POPULATION

The safety population will be the primary analysis population for all endpoints and includes all eyes that receive study treatment. However, if there are a significant number of missing values (>5% eyes with missing data at the time point of stability), an intent-to-treat (ITT) population will be used as the primary analysis population for the primary effectiveness endpoints. In this case, missing data will be imputed.

#### 20.2 PRIMARY STUDY ENDPOINTS

All primary effectiveness and safety endpoints will be evaluated at the stability timepoint.

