#### **DATA ANALYSIS:**

All endpoints will be evaluated at the refractive stability time point. The safety population will be the primary analysis population for all endpoints and includes all eyes that receive study treatment. However, if there are greater than 10% of eyes with missing study exams at the stability time point, an intent-to-treat (ITT) population will be used as the primary analysis population for the primary effectiveness endpoints.

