## Safety

## 1. MAINTENANCE OF BSCVA-LINES LOST

- Success criteria: <5% of eyes with a loss of >2 lines of BSCVA from preoperative
- Success criteria: <1% of eyes with haze beyond 6 months with loss >2 lines of BSCVA

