#### 6.3 DEFINITION OF THE TIME POINT OF REFRACTIVE STABILITY

The critical time point for analysis of safety and effectiveness is based on achievement of refractive stability. The criteria for determination of the point of refractive stability are as follows (per ANSI Z80.11-2012):

- At least 95% of the treated eyes have a change ≤1.00 D of MRSE and MRC between refractions performed at 1 month and 3 months after surgery or any two refractions performed at least 3 months apart
- The mean rate of change in MRSE and MRC, as determined by a paired analysis, is ≤0.5 D per year (0.04 D/month) over the same time period
- The mean rate of change in MRSE and MRC decreases monotonically over time, with a projected asymptote of zero or a rate of change attributable to normal aging
- The 95% confidence interval for the mean rate of change includes zero or a rate of change attributable to normal aging
- Stability is confirmed at least 3 months after the stability time point by a statistically adequate subgroup.

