# PRIMARY SAFETY ENDPOINTS

#### MAINTENANCE OF BSCVA

The proportion of eyes with a loss of >2 lines of BSCVA from preoperative will be <5%, the proportion of eyes with haze beyond 6 months with a loss > 2 lines of BSCVA will be <1%, and the proportion of eyes with BSCVA of 20/20 or better preoperatively and BSCVA 20/40 or worse postoperatively will be <1%. The frequency, proportion and 95% confidence intervals of eyes with BSCVA acuity line changes and eyes with each acuity line of BSCVA will be summarized at each study exam.

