#### SERIOUS, DEVICE-RELATED ADVERSE EVENTS

The proportion of eyes with serious, device-related adverse events will be <1% cumulatively. The number and proportion of eyes with serious, device-related adverse events throughout the study will be summarized.

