5 POSTOPERATIVE ANALYSES – PRIMARY ENDPOINTS

Primary effectiveness and safety endpoints will be evaluated at the stability time-point.

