5.2 PRIMARY SAFETY ENDPOINTS

Maintenance of BSCVA

The frequency, proportion and 95% confidence intervals of eyes with each acuity line of BSCVA (i.e. 20/20 or better, 20/25 or better, 20/40 or better, etc.) will be reported over time. The frequency

and proportion of eyes with BSCVA acuity line changes from preoperative (decreases of >2 lines, =2 lines, =1 line, no change, increases of =1 line, =2 lines and > 2 lines) will be summarized over time.

The success criteria for the endpoints regarding maintenance of BSCVA are achieved if the proportion of eyes with a loss of >2 lines of BSCVA from preoperative is <5%, the proportion of eyes with haze beyond 6 months with a loss > 2 lines of BSCVA is <1%, and the proportion of eyes with BSCVA of 20/20 or better preoperatively and BSCVA 20/40 or worse postoperatively is <1%.

Induced Manifest Refractive Astigmatism

Induced manifest refractive astigmatism is defined as the absolute change in manifest refractive cylinder (MRC) from preoperative. The following formula will be used to determine absolute change in MRC (rounded to the nearest 0.25 increment):

```
Absolute Change in Cylinder = |Preop MRC| - |Postop MRC|
```

The frequency, proportion and 95% confidence intervals of eyes with absolute changes in manifest cylinder from preoperative visit will be summarized in categories (increases of >2.00 D, 2.00 D, 1.75 D, 1.50 D, 1.25 D, 1.00 D, 0.75 D, 0.50 D, 0.25 D, no change, decreases of 0.25 D, 0.50 D, 0.75 D, 1.00 D, 1.25 D, 1.50 D, 1.75 D, 2.00 D, > 2.00 D) at each periodic study visit.

The success criterion is achieved if the proportion of eyes with induced manifest refractive astigmatism of >2.00 D is <5%.

Serious, Device-Related Adverse Events

The frequency and proportion of eyes with serious, device-related adverse events throughout the study will be summarized. The success criterion is achieved if the proportion of eyes with serious, device-related adverse events is <1% cumulatively.

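### The primary safety criterion on haze after 6 months falls under a rule that judges every primary endpoint at the stability time point, which may come before 6 months

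*Protocol*

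**What the plan says.** **Timing rule.** Four places set the time of evaluation. The synopsis (Data Analysis) and the opening of Protocol 20 both say: "All endpoints will be evaluated at the refractive stability time point". Protocol 20.2 says: "All primary effectiveness and safety endpoints will be evaluated at the stability timepoint". SAP 5 says: "Primary effectiveness and safety endpoints will be evaluated at the stability time-point". None lists an exception.

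**Haze criterion.** Protocol 6.1 (Safety, item 1) sets "<1% of eyes with haze beyond 6 months with loss >2 lines of BSCVA" as a success criterion. Protocol 20.2 and SAP 5.2 repeat it under maintenance of BSCVA. None of the three names a visit or window for judging it.

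**A criterion with its own time frame.** For serious device-related events, Protocol 20.2 says: "The proportion of eyes with serious, device-related adverse events will be <1% cumulatively". SAP 5.2 agrees. The haze criterion has no such wording.

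**When stability can fall.** Protocol 6.3 bases the first stability requirement on changes "between refractions performed at 1 month and 3 months after surgery or any two refractions performed at least 3 months apart". Protocol 20.5 and SAP 8 allow stability analyses at months 3, 6, 9 and 12.

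**Denominator.** Protocol 20.1 and SAP 2.1 make the safety population, meaning all treated eyes, primary for every endpoint. The switch to ITT when data are missing applies only to the effectiveness endpoints.

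**The concern.** The criterion needs observation after 6 months, while the rule places its evaluation at a time that may come earlier. Corneal haze is among the outcomes that the clinical hypothesis (synopsis and Protocol 3) says will meet its criterion. If the rule is followed as written and stability is set early, a primary safety criterion can be reported as met when no eye has yet reached the period in which the event is defined. Nothing says how to count eyes with no examination beyond 6 months, so whoever analyses the data would have to choose between met and not evaluable after the fact.

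**Working it through.** **1. The plan's own denominator.** Protocol 20.6 gives 300 evaluable eyes at stability and 10% attrition. 300 / 0.90 = 333.3, rounded up to 334 treated eyes (167 subjects). This reproduces the stated figure.

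**2. What 6 months means.** Protocol 10.2 sets 1 month = 4 weeks, so 6 months = 6 × 4 = 24 weeks (168 days). By calendar, 365.25 / 2 = 182.6 days = 26.1 weeks.

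**3. Visit windows (Protocol 10.2) against 6 months.**

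| Stability visit | Window (weeks) | Beyond 24 weeks? | Beyond 26.1 weeks? |
|---|---|---|---|
| Month 3 | 10-14 | none | none |
| Month 6 | 20-26 | last two weeks only | none |
| Month 9 | 35-43 | all | all |
| Month 12 | 44-60 | all | all |

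The month-3 window closes 24 − 14 = 10 weeks before 6 months, even on the shorter convention.

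**4. Literal result at month 3.** No eye can have the event. On all treated eyes the proportion is 0/334 = 0%, below 1% whatever the later haze rate. This requires two things: that the general rule overrides the criterion's own time frame, and that eyes never examined late count as event-free.

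**5. What a real assessment could show (illustration; true rates assumed).** Suppose all 334 eyes were examined beyond 6 months. Then 3/334 = 0.90% passes and 4/334 = 1.20% fails. With independent eyes the chance of passing is P(X ≤ 3), X binomial(334, p). With fully correlated fellow eyes, one affected subject gives 2/334 = 0.60% (pass) and two give 4/334 (fail), so it is P(S ≤ 1), S binomial(167, p).

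| Assumed true rate | Independent eyes | Fully correlated eyes | Literal rule, month 3 |
|---|---|---|---|
| 1% | 0.571 | 0.502 | 1 |
| 2% | 0.098 | 0.151 | 1 |
| 3% | 0.009 | 0.038 | 1 |

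**6. Sensitivity to the denominator (illustration).** Three events give 3/334 = 0.90% (pass) but 3/300 = 1.00% (fail). The 300 is the planned evaluable number at stability. The plan gives no number of eyes examined beyond 6 months.

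**The case against.** **The criterion's own time frame governs.** At month 3 it is as natural to call the criterion not yet evaluable as to call it met, and no text says that unexamined eyes count as event-free. The general rule is not strictly literal elsewhere either: the stability endpoint itself uses between-visit intervals and later confirmation. This stands as an open reading. But neither document adopts it, and it leaves the qualifying visits and the handling of unexamined eyes undefined.

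**Month 3 alone cannot complete the stability criteria.** Appendix A schedules the first postoperative manifest refraction at month 1, so month 3 supplies only one interval. Protocol 6.3 also requires a decreasing rate of change and confirmation at least 3 months later. This is correct: month 3 can be named the stability point but confirmed only at about month 6 or later. That confirmation may rest on a subgroup, and the month-6 window lies mostly or wholly within 6 months, so it need not bring data on late haze.

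**Late haze is already captured.** The default is 12 months of follow-up. Slit-lamp examinations are scheduled at months 9 and 12 (Appendix A), and BSCVA is listed among the periodic examinations (Protocol 10.6). Haze beyond 6 months with loss of 2 or more lines is a reportable adverse event (Protocol 11.1) that includes every eye meeting this criterion. SAP Appendix I tabulates specific adverse events cumulatively. All of this stands and limits the harm. However, the adverse event uses a wider threshold (2 or more lines rather than more than 2), no success criterion is tied to it, and the primary-endpoint rows of SAP Appendix I have none for the haze criterion.

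**Stronger readings a reader might infer.** One is that the trial is certain to pass on haze. The documents do not fix stability at month 3, and they leave not evaluable open. Another is that late haze will go unobserved. Loss of those data requires early stability and use of optional wording: Protocol 10.6 lets follow-up be shortened if extended follow-up is not needed, and Protocol 19 permits, but does not require, ending early once stability is established.

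**Conclusion.** The two statements conflict in the current text of both documents, and nothing resolves them. The conflict in wording does not depend on the data; its consequence does. With month-3 stability and a literal reading on all treated eyes, the criterion is met as 0/334 and carries no information on late haze. With month-6 stability, at most the last two weeks of the window are informative, and none by calendar months. With month 9 or 12 there is no conflict. The pass probabilities at assumed rates of 1-3%, and the comparison of 3/334 with 3/300, only illustrate what is at stake; they are not predictions for this trial. Because the criterion is a primary safety criterion and the visits it needs are already scheduled, the wording should be settled before any stability analysis is run.

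**What to change.** - In the synopsis (Data Analysis), Protocol 20 and 20.2, and SAP 5 and 5.2, exempt this criterion from the stability-time-point rule. Evaluate it cumulatively over all scheduled and unscheduled examinations beyond 6 months.
- Define 6 months once, consistently with the visit convention in Protocol 10.2 (24 weeks if the 4-week month applies), so that qualifying examinations late in the month-6 window are not discarded.
- Report the number of eyes with at least one qualifying examination, and show the proportion on that number beside the all-treated-eyes proportion. The all-treated-eyes denominator need not be replaced.
- State that the criterion is not evaluable, rather than met, if there are no qualifying examinations.
- Reconcile this with the passages on shortened follow-up (Protocol 10.6), early termination (Protocol 19) and reporting at stability (SAP 1).
- Add a row for the criterion to the primary endpoints in SAP Appendix I.

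The cost is wording in both documents and one table row, with no new visits or tests. The real downside is some loss of freedom to close the study or submit early while claiming this criterion.

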# PRIMARY EFFECTIVENESS ENDPOINTS

#### MONCULAR UCVA

The proportion of eyes achieving the target of 20/40 or better will be at least 85%. The frequency, proportion and 95% confidence intervals of eyes with each acuity line of UCVA will be summarized at each study exam.

## MRSE PREDICTABILITY (WITHIN 0.50 D AND 1.00 D OF TARGET)

The proportion of eyes with MRSE within 0.50 D of intended correction will be at least 50%. In addition, the proportion of eyes with MRSE within 1.00 D of intended correction at the stability time-point will be at least 75%. The frequency, proportion and 95% confidence intervals of eyes with achieved MRSE within 0.50 D and 1.00 D of intended will be summarized over time.

#### REFRACTIVE STABILITY

Refractive stability will be evaluated for two cohorts: a "consecutive cohort" (eyes with data at two consecutive visits) and a "consistent cohort" (eyes with data at all periodic visits through the point of stability and the confirmatory time point). At least 95% of eyes will have a change ≤1.00 D of MRSE and MRC between refractions performed at 1 month and 3 months after surgery or any two refractions performed at least 3 months apart. The frequency, proportion and 95% confidence intervals of eyes with MRSE and MRC changes ≤1.00 D, as well as ≤0.50 D, between visits will be presented.

Additionally, the mean change (paired differences) in MRSE and MRC between visits will be calculated to evaluate the additional refractive stability criteria. The mean rate of change in MRSE and MRC is to be ≤0.50 D per year (≤0.04 D/month). The mean rate of change in MRSE and MRC should decrease monotonically over time. At the point of stability, the 95% confidence intervals of the mean rate of change in MRSE and MRC between visits should include zero. Lastly, stability is to be confirmed at least 3 months after the stability time point by a statistically adequate subgroup using the same refractive stability criteria.

17NOV2015/ 3.0 35 PR/STAR-115-MIPS

# PRIMARY SAFETY ENDPOINTS

#### MAINTENANCE OF BSCVA

The proportion of eyes with a loss of >2 lines of BSCVA from preoperative will be <5%, the proportion of eyes with haze beyond 6 months with a loss > 2 lines of BSCVA will be <1%, and the proportion of eyes with BSCVA of 20/20 or better preoperatively and BSCVA 20/40 or worse postoperatively will be <1%. The frequency, proportion and 95% confidence intervals of eyes with BSCVA acuity line changes and eyes with each acuity line of BSCVA will be summarized at each study exam.

#### INDUCED MANIFEST REFRACTIVE ASTIGMATISM

The proportion of eyes with induced manifest refractive astigmatism of >2.00 D will be <5%. The frequency, proportion and 95% confidence intervals of eyes with absolute changes in manifest refractive cylinder will be summarized at each periodic study visit.

#### SERIOUS, DEVICE-RELATED ADVERSE EVENTS

The proportion of eyes with serious, device-related adverse events will be <1% cumulatively. The number and proportion of eyes with serious, device-related adverse events throughout the study will be summarized.

# Site Poolability

Baseline demographic data (age, gender, race, and contact lens wear) and baseline iDesign refractions (IDS, IDC and IDSE) will be reported by site. To assess the poolability of the sites, a one-way ANOVA will be used for continuous variables and the Chi-square test or Fisher's Exact tests will be used for categorical variables. An alpha level of 0.15 will be used to assess the site poolability.

#### **Outcome Stratification**

To evaluate the consistency of results, the primary effectiveness and safety points will be stratified by key factors at the stability point. These factors will include age group, gender, race, site, preoperative contact lens wear, preoperative iDesign spherical equivalent, preoperative iDesign sphere, preoperative iDesign cylinder, wavefront capture diameter, iris registration status, and clinically significant protocol deviations.

For comparisons across categories, a Mantel-Haenszel chi-square test for ordinal data and a Cochran-Mantel-Haenszel test for non-ordinal data will be used to compare the observed percentages across categories. Additionally, the results for each category will be compared to the target criterion for each study endpoint using chi-square goodness-of-fit test. All statistical tests and p-values will be reported as 2-sided and a significance level of 0.15 will be used to assess homogeneity of the primary safety and effectiveness endpoints for baseline and demographic variables.

17NOV2015/ 3.0 36 PR/STAR-115-MIPS

# Handling of Missing Data for Primary Effectiveness Endpoints

Missing data for ITT analyses of the primary endpoints will be imputed using multiple imputation methods using the MI and MIANALYZE procedures in SAS. Sensitivity analyses including worst-case analyses will also be performed for the primary effectiveness endpoints.

#### 20.3 ADDITIONAL ENDPOINTS

Results for mesopic contrast sensitivity with and without glare (1.5, 3, 6, and 12 cpd) and photopic contrast sensitivity without glare (3, 6, 12, and 18 cpd) will be reported using nonparametric analyses. The frequencies and proportions of eyes with each acuity line changes of binocular UCVA will be reported over time. Mean MRSE, MRS and MRC outcomes, as well as the accuracy of MRS and MRC, will be presented over time. MRC will be analyzed using both non-vector and vector methods. Keratometric analyses will include mean average keratometry, stability of average keratometry, and keratometric cylinder analyses. Mean iDesign aberrometry measurements (HOA) and changes in HOAs will be presented. The mean change in Schirmer I Tear Test (with anesthetic) measurements will be evaluated. The change in intraocular pressure over time will also be evaluated. The frequency and proportion of biomicroscopic slit-lamp findings, including corneal clarity, will be reported over time. The frequency and proportion of eyes with spontaneously reported ocular visual symptoms (non-directed) as well as analyses of the PRVSQ for PRK/LASIK PRO for subjective visual symptoms will be presented. All 13 sub-scales of the NEI-RQL will be analyzed and reported over time. Additionally, mean scores for the OSDI PRO will be analyzed and reported over time. The frequency and proportion of patient satisfaction about the study procedure from the non-validated questionnaires designed to collect patient satisfaction data prior to and following refractive corneal surgery will be summarized. The numbers and proportions of eyes with complications and adverse events and retreatment procedures will be summarized.

Results from the PRSVQ questionnaires completed following the 3-month study visit will be used for reliability validation purposes for the PRSVQ only and will not be analyzed in this study or used for AE reporting.

#### 20.4 VISUAL ACUITY CONVENTIONS AND GENERAL STATISTICS

Visual acuity data will be converted to LogMAR values prior to analysis and adjusted for the test distance used if it is not the standard distance for the chart. Manifest and cycloplegic refractive data will be adjusted for optical infinity and converted to minus cylinder format for presentation and analyses.

<sup>2 Little, R.J.A. and Rubin, D.B. (2002) Statistical Analysis with Missing Data. J. Wiley & Sons, New York

Descriptive statistics will typically include sample size (N), mean, standard deviation (SD), median, minimum (Min) and maximum (Max) as appropriate for continuous variables. For continuous variables, statistical tests (e.g., t-test) assuming normality will generally be used. For categorical data, the frequency and proportion will be reported and Fisher's exact test or Chi-square test will generally be applied.

#### 20.5 INTERIM REPORTS

#### Interim Analyses

Up to four interim analyses may be conducted to determine the point of refractive stability, when 90% of treated subjects have reached the 3, 6, 9 and 12 month visits, respectively. These analyses will only include refractive stability criteria evaluation. Interim analyses will not be disseminated to investigators/site personnel.

# CONTRAST SENSITIVITY SUBSTUDY SAMPLE SIZE

The sample size calculation for the sub-study is based on ANSI guidance (ANSI Z80.11) using non-inferiority approach. With a sample size is 65, a paired t-test with a 0.05 one-sided significance level will have over 90% power to detect the paired difference in mean contrast sensitivity is no less than 0.15 below zero when the expected mean difference is 0, assuming the non-inferiority margin equals 0.15 and the the standard deviation of the differences is 0.40.

17NOV2015/ 3.0 39 PR/STAR-115-MIPS

ABBOTT MEDICAL OPTICS INC.

PROPRIETARY

# APPENDIX A SUMMARY OF PROCEDURES REQUIRED AT EACH VISIT

	Preop	Op	1 Day	1 Wk	1 Mo	3 Mo	6 Mo	9 Mo	12 Mo/ET	Unsched.3
Examination	Days	Day	Days	Days	Weeks	Weeks	Weeks	Weeks	Weeks	
Note: 1 month = 4 weeks, 1 week = 7 days	-120 to 0 	0	1-2	5-8	3-6	10-14	20-26	35-43	44-60	
Informed consent	Х									
Demographics	Х									
Ocular and systemic medical history and concomitant medications	Х	Х	Х	Х	Х	Х	Х	Х	Х	Х
Inclusion/Exclusion criteria	Х									
Ocular/Visual Symptoms (Non-directed) 	Х	Х	Х	Х	Х	Х	Х	Х	Х	Х
PRVSQ, OSDI, NEI-RQL-42 and Satisfaction PRO Questionnaires	Х			X 	Х	X 	Х	Х	Х	$X^3$
iDesign System Measurement of refraction, aberrometry, topography, keratometry, pupillometry	х				Х	Х	Х	Х	х	X (after 1 week)
Keratometry (iDesign and auto or manual)	Х				Х	Х	Х	Х	Х	Х
Corneal topography (Humphrey/ Zeiss Atlas or Pentacam)	Х				Х	Х	Х	Х	Х	Х
UCVA-photopic, monocular, distance (ETDRS)	Х		Х	X 	Х	Х	Х	Х	Х	X (after 1 week)
UCVA-photopic, binocular, distance (ETDRS)	Х			X 	Х	Х	Х	Х	Х	
Manifest Refraction (ETDRS)	Х				Х	Х	Х	Х	Х	Х
BSCVA- photopic, monocular, distance (ETDRS)	Х				Х	X 				
Contrast sensitivity substudy (monocular distance corrected)	Х					Х	Х	Х	Х	Х
Refractive stability assessment for contact lens wearers	Х									
Anterior segment exam (biomicroscopic slit-lamp exam)	Х		Х	Х	Х	Х	Х	Х	Х	Х
Schirmer I Tear Test (with anesthetic)	Х				Х	Х	Х	Х	Х	Х
Intraocular pressure (applanation tonometry)	Х				Х	Х	Х	Х	X	Х
Pachymetry (ultrasound)	Х				Х				Х	Х
Cycloplegic refraction	Х						Х		Х	Х
Bilateral PRK Surgery		Х								
Dilated fundus exam	Х						Х		Х	Х
Complications 	Х	Х	Х	Х	Х	Х	Х	Х	Х	Х
Adverse events (Ocular  /Non-Ocular)	X 	Х	Х	Х	Х	Х	Х	Х	Х	Х
Device deficiencies/complaints	Х	Х	Х	Х	Х	Х	Х	Х	Х	X

<sup>1 All screening assessments should be performed prior to surgery. The screening period is the 120 days before surgery, up to and including the day of surgery.

keratometry) are to be performed before contact assessments (e.g. IOP and pachymetry). Cycloplegic refraction/fundus exam are to be the final procedures.

<sup>2 At 3 months or later, if there is a loss of 2 or more lines of BSCVA (≥ 10 letters) compared to the preoperative visit, a rigid contact lens over refraction (or pin hole acuity if rigid contact lens over refraction is medically inadvisable) should be performed to estimate the best poss ble corrected visual acuity.

<sup>3 At the investigator's discretion for unscheduled visits based on the reason for the unscheduled visit. Subject seen at an unscheduled visit due to an ocular visual symptom complaint should complete the PRVSQ, OSDI, and NEI-RQL.

<sup>4 Adverse event collection begins after informed consent.

<sup>5 As determined by slit lamp findings and patient reported outcomes questionnaires.

<sup>6 Examinations should be performed after removal of the bandage contact lens (if re-epithelized).

<sup>7 Two exploratory Satisfaction PROs will be administered (Pre-Op and then all other time points).

 Non-directed responses are obtained from asking the open-ended question "Are you having any difficulties with your eyes or vision?"

<sup>9 For instrument validation purposes the PRVSQ will be the only PRO conducted at week 1. At M3 the PRVSQ will be given a second time at 3M + 7 days for reliability validation. **Note:** Non-directed responses to the open-ended question "Are you having any difficulties with your eyes or vision?", followed by all patient reported outcome questionnaires, followed next by the iDesign measurement are to be obtained first in that order before any other ocular examinations. All non-contact procedures (e.g. topography and

